Component Transfusion Sites: Busy, Level 1 trauma centers from within the LITES Network will be selected based upon the ability to enroll patients with the proposed inclusion and exclusion criteria who currently utilize initial ratio based resuscitation (1:1:1 or 1:1:2) for patients at risk of large volume transfusion and are able to perform all necessary requirements for the planned prospective cohort study proposed. There is the potential for sites to differ based upon their current massive transfusion protocol and these standard practices will be documented for each site.

Primary TBI Subgroup Stratification: Presence or absence of Traumatic Brain Injury (TBI) will be the principle subgroup stratification for the study. Presence of TBI will be based upon CT imaging results (classification: subarachnoid, subdural, intracerebral hemorrhage, intracranial injury, epidural, +/- shift, multifocal with specific classification) and TBI severity will be characterized and grouped by GCS, Abbreviated Injury Severity (AIS) coding, ICD-10 head region severity scores

Linking Investigations in Trauma and Emergency Services

Task Order 2: Shock, Whole blood and Assessment of TBI (SWAT)

and Rotterdam CT scores. The data coordinating center will collect de-identified serial head CT images (first two performed) from all participating sites in patients with a head abbreviated injury score of 2 or greater (head AIS >2). These images will allow the determination of Rotterdam CT head scores to appropriately classify traumatic brain injury severity. Serial head CTs (first two) will also be assessed for progression of injury. An independent and blinded neuroradiologist from the University of Pittsburgh will provide the classification of brain injury.

Due to the nature of the population being studied, there will be patients who have clinically evident TBI but who do not have a head CT completed due to clinical intervention being a higher priority than diagnostic imaging. Often when patients require urgent clinical interventions, diagnostic scans (including CTs) are deferred until the patient is stabilized and the emergent issue is resolved. Unfortunately, this means that sometimes a patient expires during intervention, and a CT is never obtained. Therefore, patients who present in extremis with a clinically obvious TBI (eg: unhelmeted motorcyclist, falls from height, etc.) will be included in the TBI sub-group even if they do not have head CTs completed.

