Primary Study Outcome: The cohort study will be principally powered using 4 hour mortality as the primary outcome. This outcome was found to be significantly different across treatment arms in the recent PROPPR trial and early mortality time points have recently been recommended and deemed most appropriate for hemorrhagic shock clinical trials.^{24,43} Promoting survival beyond this time period may represent the critical period that is required for an injured patient to be transported to a higher echelon of care, particularly when injury occurs in austere environments.

Secondary Non-TBI Clinical Outcomes: Secondary clinical outcomes will include 12 hr mortality, 24hr mortality, 28 day mortality, time to hemostasis (defined by a WB or PRBC transfusion rate; ≤ 1 unit/hour and surgeon directed intraoperative assessment), death from exsanguination/hemorrhage, blood and blood component transfusion requirements (over 1st four hours and total at 24hrs), Multiple Organ Failure, nosocomial infection, transfusion reaction, venous thromboembolism (VTE), ICU free days and ventilator free days.

TBI Specific Outcomes: For the overall TBI subgroup, the principle outcome will be 6 month Extended Glasgow Outcome Scale (GOS-E). Additional TBI specific outcomes will include hemodynamic parameters (serial systolic and diastolic blood pressure and heart rate measurements), prehospital, arrival, serial and discharge Glasgow Coma Scale scores, need for craniectomy/craniotomy, need for mannitol administration, need for paralysis, need for barbiturate coma, need for hypertonic saline administration, need for ICP monitoring, ICP pressures (initial, max daily x 7 days), TBI progression based upon serial CT imaging in initial 48 hours and Galveston Orientation and Amnesia Test (GOAT score) at discharge. Each accrual site will transfer the TBI patient's name, contact information, and basic injury characteristics, GOAT results, and discharge disposition to the Clinical Coordinating Center in Pittsburgh.

Linking Investigations in Trauma and Emergency Services

Task Order 2: Shock, Whole blood and Assessment of TBI (SWAT)

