Death from Exsanguination/Hemorrhage: Those patients who succumb on the operating table, IR suite or ICU due to uncontrolled coagulopathy or hemorrhage in the first 4 hours from arrival will have their mortality classified as exsanguination/hemorrhage. This will be determined by the individual trauma surgeon at the time of the event.

Acute Hemolytic Transfusion Reaction: We will utilize and characterize acute hemolytic transfusion reactions as defined by the CDC/National Healthcare Safety Network (NHSN) Hemovigilance Surveillance definition (www.cdc.gov/nhsn).

Linking Investigations in Trauma and Emergency Services

Task Order 2: Shock, Whole blood and Assessment of TBI (SWAT)

Galveston Orientation and Amnesia Test (GOAT): For TBI subjects, we will obtain the GOAT score at the time of discharge and the calculated score per standard methods.⁴⁸ (Figure 4) GOAT is a 10-item questionnaire used to quickly assess post-traumatic amnesia following head injury. The GOAT is read orally to the patient and may be easily administered at the bedside. The total score accounts for orientation of person, place, and time, and recollection of events pre and post-injury. Cutoff scores are available to identify abnormal, borderline, and normal orientation and it will additionally determine if a subject is able to provide continuing participation consent if consented by proxy.

Extended Glasgow Outcome Scale (6 months-GOSE): For TBI subjects, the GOSE score will be obtained at 6 months +/- 1month by hone survey or direct patient contact, whichever is feasible. For those TBI subjects who were unable to consent at discharge, the GOAT will be administered to assess their ability to provide direct consent, prior to the administration of the GOSE. When the assessment is done by phone, the verbal consent of participants who have regained the ability to consent, will be obtained to allow the GOSE to be completed. The score is able to characterize 6 month functional status into 8 well defined categories as shown in (Figure 5).

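### Unscanned patients can enter the TBI subgroup without a stated neurological criterion, so some early deaths without TBI may count as GOS-E 1, unevenly by arm if whole blood changes early mortality

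*Combined protocol and SAP*

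**What the plan says.** Under Primary TBI Subgroup Stratification the general rule is "Presence of TBI will be based upon CT imaging results". The next paragraph explains that in unstable patients "diagnostic scans (including CTs) are deferred until the patient is stabilized and the emergent issue is resolved", and that "sometimes a patient expires during intervention, and a CT is never obtained". It then makes an exception: "patients who present in extremis with a clinically obvious TBI (eg: unhelmeted motorcyclist, falls from height, etc" and similar cases "will be included in the TBI sub-group even if they do not have head CTs completed". Both examples are mechanisms. The exception names no GCS, pupil, examination or autopsy criterion, and nobody is assigned to adjudicate it. The blinded neuroradiologist described in the same section works from CT images and so cannot classify these patients.

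Under TBI Specific Outcomes, "For the overall TBI subgroup, the principle outcome will be 6 month Extended Glasgow Outcome Scale (GOS-E"). Of that scale the plan says "The score is able to characterize 6 month functional status into 8 well defined categories". Category 1 in Figure 5 is death, with no restriction by cause.

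The Analyses section (Hypothesis 1C, Aim 2 and Subgroup Analysis) does not flag or count unscanned patients, and it plans no alternative version of the subgroup.

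**The concern.** Take two patients without brain injury who have the same mechanism and the same presentation in extremis. One stabilises, has a negative CT and is outside the TBI subgroup. The other dies before CT, may be judged to have clinically obvious TBI, and then enters the subgroup with GOS-E 1. For such patients membership turns on early death, and 4-hour mortality is the study's primary outcome.

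The entry criteria make missed scans plausible, because every patient goes to the operating room or interventional radiology within 60 minutes of arrival. If whole blood lowers early mortality, fewer misplaced deaths fall in the whole blood arm. The GOS-E comparison in Hypothesis 1C then moves towards whole blood without any effect on the brain. The same deaths enter the whole blood-by-TBI interaction described under Subgroup Analysis.

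**Working it through.** **The plan's own figure.** Expected TBI subgroup: 0.35 × 1,190 = 416.5, which rounds to the stated 417. The Power Analysis also gives 892 consented patients, for which 0.35 × 892 = 312. I show results for both totals.

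**Inputs from the Power Analysis.** Control 4-hour mortality 0.111; hazard ratio 1.9; three whole blood and three component sites, taken as equal arms; two-sided 0.05.

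**Assumptions, not in the documents.**
- The hazard ratio of 1.9 is a benefit of whole blood, so whole blood mortality is 1 − (1 − 0.111)^(1/1.9) = 0.060.
- Among true TBI patients, 35% have GOS-E 1. The other seven categories have shares of 3%, 12% and five times 10%, identical in both arms.
- A share u of 4-hour deaths is misplaced, meaning added to the subgroup as GOS-E 1 on top of the true TBI patients.

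**Formula per arm of size n with mortality p.** Added deaths = n·p·u. True TBI patients T = 0.35(n − n·p·u). GOS-E 1 share = (n·p·u + 0.35T)/(n·p·u + T).

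Example at u = 50% and n = 595:
- Component: 595 × 0.111 × 0.5 = 33.0 added; T = 0.35 × 562.0 = 196.7; share = (33.0 + 68.8)/229.7 = 44.3%.
- Whole blood: 595 × 0.060 × 0.5 = 17.9 added; T = 0.35 × 577.1 = 202.0; share = (17.9 + 70.7)/219.9 = 40.3%.

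The false-positive rate comes from 5,000 simulated studies per setting, using a tie-corrected Wilcoxon test without clustering or covariates.

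| u | Added deaths, component vs whole blood (N = 1,190) | GOS-E 1 share | Difference (points) | False-positive rate, N = 1,190 | False-positive rate, N = 892 |
|---|---|---|---|---|---|
| 0 | 0 vs 0 | 35.0% vs 35.0% | 0 | 0.052 | 0.049 |
| 10% | 6.6 vs 3.6 | 37.0% vs 36.1% | 0.9 | 0.051 | 0.054 |
| 25% | 16.5 vs 8.9 | 39.9% vs 37.7% | 2.2 | 0.067 | 0.063 |
| 50% | 33.0 vs 17.9 | 44.3% vs 40.3% | 4.0 | 0.127 | 0.102 |
| 75% | 49.5 vs 26.8 | 48.4% vs 42.7% | 5.7 | 0.200 | 0.155 |

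Whole Blood Transfusion Sites gives a whole blood share of 33% instead of equal arms. With that share and N = 1,190, the rates for u = 10% to 75% are 0.054, 0.064, 0.112 and 0.183.

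**A moderate case.** Suppose 30% of 4-hour deaths are unscanned and labelled TBI, and half of these have no TBI, so u = 0.30 × 0.50 = 15%. With 446 per arm, 446 × 0.111 × 0.15 = 7.4 and 446 × 0.060 × 0.15 = 4.0 deaths are misplaced, beside 156 true TBI patients per arm with 0.35 × 156 = 54.6 deaths. The shares are (7.4 + 54.6)/163.4 = 37.9% and (4.0 + 54.6)/160.0 = 36.6%, a gap of 1.3 points. A simulation of this case with 40,000 runs gave a false-positive rate of 0.057.

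**What the larger values of u require.** If 65% of labelled unscanned deaths have no TBI (the complement of the plan's 35%), then u = 25% needs 0.25/0.65 = 38% of all 4-hour deaths to be unscanned and labelled TBI, and u = 50% needs 0.50/0.65 = 77%.

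**Equal early mortality.** With 11.1% in both arms and u = 50%, the false-positive rate stayed between 0.044 and 0.055 over both totals and both allocations. The added deaths then dilute the comparison but do not inflate type I error.

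The size of the effect on the interaction was not calculated.

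**The case against.** A reader might infer that mechanism alone admits a patient, or that only patients who die are admitted. The text supports neither. It requires presentation in extremis and a clinically obvious TBI, and offers the mechanisms as examples. It is worded by state at presentation, and death before CT is only the reason given. The gap is that nothing states what makes a TBI clinically obvious. The dependence on death arises because stabilised patients are scanned later.

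A reader might also infer that this rule is what brings hemorrhage deaths into GOS-E. It is not. Early deaths from "uncontrolled coagulopathy or hemorrhage in the first 4 hours from arrival will have their mortality classified as exsanguination/hemorrhage", but that outcome is separate and removes nobody from GOS-E. A patient with CT-proven TBI who exsanguinates scores 1 under any subgroup definition. Only deaths of patients without TBI are misplaced.

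Further points for the plan stand. Some unscanned deaths will be true TBI, and leaving out all unscanned patients would select on survival to CT, so the exception is a reasoned choice. ED deaths are excluded, both examples are blunt mechanisms, and the cohort also takes penetrating injury. All three limit the number affected. The Power Analysis asks for caution with secondary findings. Cause of death is classified, with hemorrhage separate from TBI/herniation, so the material to examine the question exists.

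These points reduce the likely size. They do not supply a criterion, a count or a second version of the result.

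**Conclusion.** The concern holds as a limited one. The exception has no neurological criterion, and membership of a patient without TBI can turn on dying before CT. If whole blood changes early mortality, the resulting misclassification is uneven between arms and reaches Hypothesis 1C and the TBI interaction.

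Its size is unknown because the documents give no unscanned share. Under the assumptions above it is negligible when 10–15% of 4-hour deaths are misplaced. It becomes noticeable at 25% and material at 50%, and type I error is not inflated if early mortality is equal. The stronger conclusion that the TBI result is seriously biased is not supported, since it needs a large share of all 4-hour deaths to be unscanned, labelled TBI and free of TBI. This is a worthwhile improvement and does not threaten the primary analysis.

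**What to change.** Prespecify one rule for probable TBI from data recorded at arrival, for example GCS and mechanism, and apply it alike to scanned and unscanned patients whether or not they survive to CT.

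Report the TBI-subgroup GOS-E result and the whole blood-by-TBI interaction in three versions:
1. the plan's current definition;
2. the arrival-based rule, noting that shock can lower GCS and so admit patients without TBI;
3. CT-confirmed patients only, noting that this selects on survival to CT.

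Report the number of unscanned patients in the subgroup and their cause of death by arm. If the versions differ materially, describe the TBI conclusion as sensitive to the subgroup definition. Agreement should not be a condition for drawing a conclusion, because the CT-only version can differ for a legitimate reason when whole blood affects early survival.

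The cost is a few extra analyses. Mechanism, prehospital and ED GCS, and cause of death are already collected (Data Collection; Classification of Mortality).

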Hypothesis #1B: *Whole blood resuscitation will be associated with a lower incidence of 12 hour and 24 hour mortality, a lower incidence of death from exsanguination, incidence of MOF, nosocomial infection, improved transfusion ratios, lower overall blood transfusion requirements and shorter time to hemostasis as compared to those resuscitated with component therapy.*

Hypothesis #1C: *Whole blood resuscitation will be associated with an improved Glasgow Outcome Score-Extended at 6 months post injury as compared to those resuscitated with component therapy in patients with traumatic brain injury.*

Hypothesis #2A: *A nadir prehospital and acute phase resuscitation systolic blood pressure greater than or equal to 120 mmHg will be associated with improved traumatic brain injury outcomes at discharge and at 6 months.*

Linking Investigations in Trauma and Emergency Services

Task Order 2: Shock, Whole blood and Assessment of TBI (SWAT)

Hypothesis #2B: *The magnitude of the dose depth curve of systolic blood pressure during the prehospital and acute phase resuscitation will be associated with neurological outcome differences at discharge and at 6 months following traumatic brain injury.*

Research Design and Methods

Study Design: The LITES Network will perform a multicenter, prospective, observational cohort study over a 4 year period to determine the impact of whole blood resuscitation in trauma patients with hemorrhagic shock at risk of large volume resuscitation with and without TBI. Early whole blood resuscitation will be compared to standard component resuscitation. The study will also further characterize blood pressure and resuscitation endpoints in poly-trauma patients with traumatic brain injury. Six trauma sites with appropriate characteristics will be selected from network sites across the country. (Figure 2)

Figure 2

Study Setting: The study will be performed utilizing busy level I trauma centers from within the LITES Network located across the country, at sites where either whole blood has currently been incorporated into standard of care or where component blood transfusion is being utilized for patients in hemorrhagic shock at risk for large volume resuscitation. Due to the paucity of trauma centers who are currently utilizing whole blood for trauma patients as standard of care, the potential to incorporate additional sites may be required over time.

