Suicidal or emotionally distressed participants: If a participant reports suicidal ideation during the GOS-E, a risk assessment will be performed immediately by a trained neuropsychological technician under the supervision of a licensed neuropsychologist. If the participant is found to NOT be at imminent risk, resources will be given to the participant in the form of the Suicide Hotline and The Brain Injury Association of America website URL. The technician will compose a 'Note To File' detailing their assessment and will make the other study team members aware of their assessment. If the participant is found to be at imminent risk, the technician will encourage the participant to go to their nearest local emergency room. These actions will be noted in the case file.

Predefined Subgroups: Predefined subset analyses in addition to principle TBI subgroup analysis will be performed looking at 1) patients enrolled from the scene of injury versus those enrolled from a referral hospital, 2) patients with a preinjury history of vitamin K antagonist medication versus those without, 3) patients with preinjury history of antiplatelet medication versus those without, 4) patients with preinjury history of novel anticoagulant use versus those without, 5) patients who ultimately did or did not require massive transfusion (≥ 10 units blood in first 24hrs), 6) patients who ultimately did or did not meet a critical transfusion threshold of ≥ 4 units PRBCs or whole blood in a 2 hour time period, 7) patients who ultimately did or did not require ≥ 6 units blood in first 24hrs, 8) patients who did or did not receive leukocyte reduction WB products, 9) TBI patients who did or did not receive a craniectomy/ craniotomy, 10) TBI patients who did or did not require ICP monitoring. It is recognized that the study is not appropriately powered for these subgroup comparisons and the results and conclusions formulated from these subgroup analyses will be considered exploratory in nature and will not be used as a basis for treatment recommendations.

Specific Outcome Definitions:

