Sample Tracking, Management and Storage: After sample obtainment, processing and storage, samples will initially be batched sent to the University of Pittsburgh biological sample repository where it will be tracked, managed and stored until the necessary translational or mechanistic measurement are performed. The CCC and DCC have a long track record of coordinating such processes.

Power Analysis: The prospective cohort study will utilize time to 4 hour mortality for its primary outcome to power the study. Based upon the 6 LITES Network sites admission history that will be utilized and their respective volume of hemorrhagic shock patients meeting inclusion and exclusion criteria and a 3.5 year enrollment time period, we plan to initiate sampling on 1,050 patients over the enrollment time period of the study. With an 85% consent rate which is an estimate based upon prior studies of similar nature, we will consent for participation 892 patients for the study. With an estimate baseline rate of 4 hour mortality of 11.1 % derived from the PROPPR study, there will be 90% power to detect a hazard ratio of 1.9.

Calculations are based on the primary aim of the study based on the following assumptions:

- Type I error rate of 0.05
- Two-sided alternative hypothesis

Linking Investigations in Trauma and Emergency Services

Task Order 2: Shock, Whole blood and Assessment of TBI (SWAT)

- 6 sites will be involved, three whole blood and three component sites
- Each site will enroll 175 participants in 3.5 years of enrollment, of which, 85% will be eligible for the study (149)
- The calculations are based on Cox proportional hazard model
- A 4 hour event rate in the control (non-whole blood) group of 0.111

The power calculations for these secondary aims are presented below. When reporting the results of the analyses, caution will need to be taken with respect to the interpretation of the findings since they are secondary in nature.

The secondary outcomes in Aim 1B include binary outcome, continuous outcomes, and time to event outcomes. For the binary outcomes, the odds ratio that can be detected is presented in Table 1. For the continuous outcome, the effect size that can be detected is 0.13. Finally, for the time to event outcomes, the hazard ratio that can be detected over a range of event rates in the control group is also presented in Table 1.

Event Rate	.1	.2	.3	.4	.5	.6
Odds Ratio	1.76	1.56	1.49	1.46	1.46	1.48
Hazard Rate	2.69	1.70	.37	.30	.27	.30

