model will be generated using the area under the curve as the dependent variable and the baseline characteristics as independent variables to generate an estimated area under the curve (propensity score) for each subject. The population will then be separated into five strata of equal sample size, based on the propensity. Within each stratum, the association of the area under the curve with outcome will be assessed using a hierarchical polytomous logistic regression model (outcome: GOS-E at six months, independent variable: area under the curve).

To determine the association across strata and if the association differs across strata, a multinomial polytomous regression model with GOS-E at six months as the outcome, area under the curve, an indicator of stratum, and the two-way interaction as independent variables will be fit.

The same analytic approach will be used to measure outcomes at discharge except a hierarchical logistic regression model will be used.

Subgroup Analysis: The general approach to assess the homogeneity of a treatment effect across subgroup will be to include an interaction term between the treatment variable and the characteristics defining the subgroup in the regression model. A statistically significant interaction term would indicate that the null hypothesis of a homogenous effect would be rejected indicating a differential effect of the treatment across the subgroups. For example, when examining the homogeneity of the effect of whole blood on the primary outcome among those with and without a traumatic brain injury, the hierarchical logistic model will be modified to include a main effect for traumatic brain injury and the two-way interaction between whole blood use and traumatic brain injury.

[figure not shown]

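### Subgroups 5–7, 9 and 10 are fixed after exposure, so whole-blood effects within them can be biased, and the subgroup 8 interaction cannot be estimated

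*Combined protocol and SAP*

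**What the plan says.** The Predefined Subgroups section lists ten subgroups besides TBI. Numbers 1–4 (scene or referral, and three kinds of preinjury medication) are known before exposure. The others are not:

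- 5: "patients who ultimately did or did not require massive transfusion", with a cut at 10 units in 24 h. Subgroup 6 uses 4 units of red cells or WB within 2 h, and subgroup 7 uses 6 units in 24 h.
- 8: "patients who did or did not receive leukocyte reduction WB products".
- 9 and 10: TBI patients with or without craniectomy/craniotomy, and with or without ICP monitoring.

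The Subgroup Analysis section gives one general method for all of them, which is to "include an interaction term between the treatment variable and the characteristics defining the subgroup in the regression model". It makes no exception for any subgroup. Hypothesis #1B expects WB to be associated with "lower overall blood transfusion requirements". The Predefined Subgroups section adds that the study is not powered for these comparisons, that they are exploratory, and that they will not support treatment recommendations.

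**The concern.** A subgroup is safe for comparing treatments when membership cannot depend on treatment or on the outcome. Here it can depend on both. If WB lowers the number of units, a WB patient who still reaches 10 units is on average more severely injured than a component patient who does. The WB patients who drop below 10 units are also sicker than the component patients already there, so both strata compare unlike patients. The 24 h thresholds are also applied to a 4 h mortality outcome, and a patient who dies early has less time to accumulate units. Subgroup 6 goes further: WB units, the exposure itself, count towards membership.

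At stake is a published WB effect within heavily transfused patients, or within patients with ICP monitoring, that reflects sorting and not benefit or harm. For subgroup 8 the planned model cannot be fitted as written.

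**Working it through.** **1. The plan's own figure.** The plan gives no power or size figure for subgroups. The nearest is the primary calculation: "Type I error rate of 0.05", "Two-sided alternative hypothesis", "there will be 90% power to detect a hazard ratio of 1.9", and "we will consent for participation 892 patients for the study". Events needed = 4(1.960 + 1.282)² / (ln 1.9)² ≈ 102.0, so 103. With the 4 h rate of 0.111 applied to everyone, 892 × 0.111 = 99 events, and power = Φ(0.642 × √99 / 2 − 1.960) = 89.1%. That reproduces the stated 90%. The plan calls 0.111 the control rate; read that way, with WB protective at 1/1.9, there are 76 events and power is 80.0%. That is a separate matter. Only N = 892 and the rate 0.111 are used below.

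**2. Subgroup definers set against outcomes.**

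| Subgroup | Defined by | Also an outcome under |
|---|---|---|
| 5, 7 | units in 24 h | Secondary Non-TBI Clinical Outcomes (units at 4 h and 24 h); Hypothesis #1B |
| 6 | units in a 2 h period | built from the same quantity |
| 9 | craniectomy/craniotomy | TBI Specific Outcomes |
| 10 | ICP monitoring | TBI Specific Outcomes |

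**3. Can bias arise with no WB effect on death?** Every input here is an assumption. Exposure is assigned at random. Severity is s ~ N(0,1). The death logit is −2.6 + s in both arms. Units are Poisson with mean exp(1.8 + 0.6s), multiplied under WB by 0.8 or 0.67. The overall OR for death is 1.00.

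| WB multiplier | Death limits units? | OR, ≥10 units | OR, <10 units |
|---|---|---|---|
| 0.8 | no | 1.22 | 1.16 |
| 0.67 | no | 1.43 | 1.27 |
| 0.8 | yes (mean × uniform 0–1 / mean halved) | 1.08 / 0.92 | 0.97 / 0.98 |
| 0.67 | yes (same two forms) | 1.17 / 0.85 | 0.96 / 0.96 |

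The limit applies to the mean units of patients who die.

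**4. Range over other assumptions.** Mortality is set to 0.111. The severity slope for death is 1.2, 2 or 3. Units are overdispersed (gamma–Poisson, shape 4) with mean 6·exp(0.7s) or 6·exp(1.0s). Units in patients who die are either left alone or scaled by a uniform factor from 0.1 to 0.6. The cut is at 10 units and the true OR is 1.0. The last column is the share of simulated studies of 892 with a significant WB effect inside a stratum, nominally 5%.

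| WB multiplier | Death limits units? | OR, ≥10 | OR, <10 | False positives |
|---|---|---|---|---|
| 0.8 | no | 1.17–1.24 | 1.11–1.30 | 6–12% |
| 0.8 | yes | 0.93–1.04 | 0.96–1.05 | 2–5% |
| 0.6 | no | 1.43–1.68 | 1.26–1.76 | 13–43% |
| 0.6 | yes | 0.85–1.11 | 0.93–1.10 | 1–7% |
| 0.4 | no | 1.96–2.72 | 1.43–2.50 | 25–80% |
| 0.4 | yes | 0.70–1.23 | 0.89–1.15 | 2–9% |

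If WB changes neither units nor mortality, both ORs are 1.00.

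**5. The planned interaction test.** From step 3 without the limit, the ratio of stratum ORs is 1.22 / 1.16 = 1.05 (log 0.05) or 1.43 / 1.27 = 1.13 (log 0.12). At N = 892 the standard error of the log ratio is about 0.47–0.50, so the false shift is 0.05 / 0.47 ≈ 0.1 to 0.12 / 0.50 ≈ 0.24 standard errors. Over all settings in step 4 the test rejected in about 2–10% of runs.

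**6. Subgroup 8.** Let L = 1 for a patient who received leukoreduced WB. The columns of the model are (1, WB, L, WB×L), and only three patterns can occur: component-only (1,0,0,0), WB not leukoreduced (1,1,0,0), and WB leukoreduced (1,1,1,1). WB×L equals L in every row, so the rank is 3 for 4 columns and the interaction cannot be separated from L. This is algebra and needs no assumption. What remains estimable is leukoreduced against non-leukoreduced among WB recipients. The Whole Blood Transfusion Sites section says leukoreduction may differ by site. If it is fixed by site, adding L to six site intercepts gives 7 columns of rank 6, so even that contrast cannot be separated from fixed site effects.

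**The case against.** The plan already calls these analyses underpowered and exploratory and bars treatment recommendations from them. That limits the consequences and is a fair reason not to rank this point higher. It does not answer the point: low power is imprecision, whereas this is systematic error that a larger sample would not remove, and no label makes a rank-deficient term estimable.

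A reader might infer that the plan will produce false subgroup interactions. The numbers do not support that: the bias often runs the same way in both strata, and the interaction test is barely moved. A reader might also infer that WB will be made to look harmful. That follows only if death does not limit units; once it does, the bias mostly shrinks or changes direction.

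It would likewise be too strong to say that patients who die early cannot reach the thresholds. ED deaths are excluded, entry requires transfusion within 60 minutes of arrival, and some early deaths will meet 4 units in 2 h.

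For 9–10, no hypothesis states a WB effect on craniectomy/craniotomy or ICP monitoring, so no magnitude can be claimed. For subgroup 8, a comparison within WB recipients is a natural reading of the list; but the Subgroup Analysis section gives only the interaction, so the text needs correcting.

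**Conclusion.** The point holds in a limited form. Subgroups 5–7, 9 and 10 are determined after exposure and are, or are built from, the plan's own outcomes, so WB effects within them can be biased under a true OR of 1.0. For 5–7 the plan's own Hypothesis #1B supplies the mechanism. The illustrative sizes in step 3 rest on an assumed 20–33% reduction in units, an assumed severity model and an assumed effect of death on units. They show that the bias can matter, not what it will be in this study. For 9–10 the objection is one of structure.

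Subgroup 8 is the firmest part: the interaction as written is not estimable, whatever the data. That does not mean leukoreduction cannot be studied, since the comparison within WB recipients remains, subject to confounding with site. Nothing here touches the primary analysis or subgroups 1–4. This is a cheap improvement that should be made.

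**What to change.** Amend the Predefined Subgroups and Subgroup Analysis sections:

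- **5–7:** base the inferential subgroup on transfusion need predicted from characteristics measured before the first transfusion and already collected, such as mechanism and the earliest prehospital SBP and heart rate. Arrival vitals are less safe, because prehospital transfusion is allowed and recorded, so they can follow exposure. Use FAST only if the eligibility record is kept, since it is an entry criterion but is not named in the data lists.
- **9–10:** use the first recorded GCS or head AIS.
- **Present splits for 5–7, 9 and 10:** keep as descriptive only, and state that no within-stratum WB effect will be interpreted.
- **8:** restate as leukoreduced against non-leukoreduced among WB recipients, with no interaction term, and say that it may be confounded with site.

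The cost is SAP wording plus a simple prediction model. There are two downsides. The familiar massive-transfusion split becomes descriptive. The predicted-need strata will also have a restricted range, because SBP, heart rate and mechanism are entry criteria too.
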